11.7 Where and how data or specimens will be stored?

Response: Data will be stored securely and backed up regularly at the University at Buffalo School of Nursing in room 301B Wende Hall, [name]. To ensure data safety, data entry will be performed on a protected computer, secured by the University at Buffalo Standards for Securing Regulated Private Data and the New York State Information Security Breach Notification Act with access limited by UBIT safety policies to data management, including: secure server and computer, base encryption, UBIT password and name account verification and daily electronic secure back up.

11.8 How long the data or specimens will be stored?

Data will be stored for a minimum of three years and data destruction will be manually performed in accordance with the applicable institutional schedule at the end of its life cycle. Each team member will access the data following the University at Buffalo Standards for Securing Regulated Private Data as mentioned above.

11.9 Who will have access to the data or specimens?

Members of the research team who have completed the required SUNY Buffalo CITI training will have access to data with UB secure access generated by UBIT password via authorized UB computers at University at Buffalo School of Nursing.

11.10 Who is responsible for receipt or transmission of the data or specimens?

The principal investigator and research assistant will be responsible for receipt of the data from participants. Once data is de-identified, data coders will code, enter, verify and analyze the data under the direction of the PI. This study will not use specimens.

11.11 How data and specimens will be transported?

Response: De-identified survey data will be transported by the PI in a briefcase.

12.0 Provisions to Monitor the Data and Ensure the Safety of Subjects

12.1 Describe the plan to periodically evaluate the data collected regarding both harms and benefits to determine whether subjects remain safe.

The PI will be responsible for ensuring data integrity and safety monitoring for human subjects and communicating any negative outcomes or any serious events to the IRBs and other offices/agencies. Because of the minimal to low risk associated with this protocol, the data safety and monitoring plan (DSMP) for this project involves close monitoring by the principal investigator (PI) and a safety officer, an Nurse Practitioner in the School of Nursing. The data safety monitoring team will ensure participant safety, ensure the validity and integrity of the data, monitor study progress, and make recommendations regarding appropriate protocol and operational changes which may have substantial effects upon the ultimate interpretation of the study. They will also be responsible for promptly report any serious adverse events to the Institutional Review Boards (IRB) at Roswell Park Cancer Institute, the VA Western New York Health Systems (VA WNYHS) and the University at Buffalo

Weekly reviews of participant accrual will be conducted by the PI during weekly research meetings. If participant accrual and/or retention drop below what is required for successful completion of this study, the PI will alert the statistician and strategies will be developed to overcome the identified problems. Records from subjects recruited during that week will also be scrutinized to insure that all participants are eligible for participation in the study. The PI and members of the research team will be monitoring developments in the literature and results of related studies that may have an impact on the safety of participants or on the ethics for the research study. Additionally, [name], a sleep research expert and consultant, will serve as a resource for new findings in the field and to assist with this clinical trial.

12.2 Describe what data are reviewed, including safety data, untoward events, and efficacy data.

Data review includes eligibility, referral for sleep apnea, referral for low oxygen during sleep, completion of data collection instruments, adherence to intervention, number of follow up phone calls accepted, and outcome measures of efficacy: fatigue, sleep and circadian activity rhythms. Daytime sleepiness will also be evaluated daily, but monitored weekly.

12.3 Describe how the safety information will be collected (e.g., with case report forms, at study visits, by telephone calls with participants).

Daytime sleepiness may be hazardous for patients at risk for falling asleep while driving, for example. This is a safety question that is monitored

daily and assessed weekly by telephone with the participant. It is also assessed at baseline and end of study with the Epworth Sleepiness Scale.

12.4 Describe the frequency of data collection, including when safety data collection starts.

Data collection will occur during and immediately following the screening process, and will continue throughout the intervention period (1-week), concluding with the post intervention data collection period (2-weeks). Data collection will be conducted approximately weekly, to include a safety question. The daytime sleepiness question is important to determine if participants are at risk for harm.

12.5 Describe who will review the data.

The PI will review the data for completeness, accuracy and safety. A second team member will code, enter, and then verify the data with a third member of the research team.

12.6 Describe the frequency or periodicity of review of cumulative data.

Cumulative data will be reviewed monthly by the PI. Data coding and entry errors will be identified and corrected.

12.7 Describe the statistical tests for analyzing the safety data to determine whether harm is occurring.

If a participant scores >10 on the Epworth Sleepiness Scale or scores a 3 or higher on the daily sleepiness scale, we will discuss this result with the participant to determine if they are at risk for harm and monitor the patient more frequently.

12.8 Describe any conditions that trigger an immediate suspension of the research.

Response: We do not anticipate any condition that would trigger an immediate suspension of the research.

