7.0 Study Timelines

7.1 *Describe the duration of an individual subject's participation in the study.*

Subjects will be expected to participate for approximately 10 weeks during which ApneaLink screening, completion of pre-intervention data collection, 1 week for intervention, and completion of post-intervention data collection will occur.

7.2 *Describe the duration anticipated to enroll all study subjects.*

Approximately 18 months.

7.3 *Describe the estimated date for the investigators to complete this study (complete primary analyses)*

December, 2017.

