11.0 Data Management

11.1 Describe the data analysis plan, including any statistical procedures.

Hypothesis testing will be conducted using 2x2 ANOVAs for the first specific aim, with Logistic Regressions for the second specific aim (predicting treatment response and non-response) and with Linear and Logistic Regressions for the third specific aim (predicting illness severity and treatment response).

11.2 Provide a power analysis.

Response:

The primary outcome for sleep is the sleep efficiency score. Previous research has indicated that persons with satisfactory sleep have a sleep efficiency score exceeding 85, whereas persons reporting unsatisfactory sleep have a score at most 70, with both groups reporting a standard deviation of approximately 15. The estimated effect size from this study

is 1. The goal of this study is to improve sleep efficiency from an unsatisfactory level to a satisfactory level. Using a large effect size of .08 with a one-tailed significance of .025 and power of 80%, the required sample size for the two-group comparison is 26 per group for a total sample of 52.

11.3 Describe the steps that will be taken to secure the data (e.g., training, authorization of access, password protection, encryption, physical controls, certificates of confidentiality, and separation of identifiers and data) during storage, use, and transmission.

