be recruited over 2 years. Not all lung cancer survivors have sleep continuity disturbance, but in our current sleep study, we were able to recruit 20 lung cancer survivors with insomnia within 6 months at Roswell Park Cancer Institute. Retention rate of study participants is anticipated to be 80% based on our previous experience. Oversampling will result in the desired target sample size at this rate. At the time of enrollment in the study, three forms of contact information will be obtained, email address, telephone number, and address for delivery of the data collection instruments and return mailers. In addition, an alternate contact person will be obtained to help decrease loss to follow up due to the length of the study.

20.3 Describe the time that you will devote to conducting and completing the research.

Response: 20% of the PI's research time, 10% of the Co-I's time and the RA will work 10 hours/week on this study.

20.4 Describe your facilities.

Response: Recruitment Site: Roswell Park Cancer Institute (RPCI) was founded in 1898 is America's first cancer center and holds the National Cancer Institute designation of "comprehensive cancer center." RPCI has 133 hospital beds and 12 multidisciplinary clinics and is the only comprehensive cancer center of Western New York area. As a member of the prestigious National Comprehensive Cancer Network, RPCI has played a vital part in setting clinical guidelines for the care of Oncology patients. RPCI plays a pivotal part in cancer research with several ongoing funded research projects.

The thoracic clinic provides state of the art comprehensive multidisciplinary care to approximately 700 patients with lung cancer annually. The presence of several specialties -pulmonary medicine, medical oncology and thoracic surgery along with the undiagnosed clinic in a single location with additional support from nearby radiation oncology clinics and interventional radiation ensures excellent patient care and satisfaction. The patients with lung masses and suspected lung cancer are promptly seen by the pulmonary clinic or the undiagnosed clinic and scheduled for diagnostic biopsy procedures. Several multidisciplinary meetings are conducted each week to make complicated management decisions for the patients.

The VA WNYHS provides care to approximately 100 newly diagnosed veterans with lung cancer annually.

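### The monthly review of cumulative data is not stated to be blind to arm, and the end of enrolment is inconsistent, so nothing rules out an interim efficacy look.

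*Combined protocol and SAP*

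**What the plan says.** **Monitoring.**
- Section 12.2 lists among the data reviewed the "outcome measures of efficacy: fatigue, sleep and circadian activity rhythms".
- Section 12.6 gives the frequency: "Cumulative data will be reviewed monthly by the PI".
- Section 12.1 names a monitoring team of the PI and a safety officer. Its tasks include making "recommendations regarding appropriate protocol and operational changes which may have substantial effects upon the ultimate interpretation of the study".
- Section 12.5 gives the aims of the PI's review as accuracy, completeness and safety. Section 12.6 goes on to the correction of coding and entry errors.

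**Error rate.** Section 11.2 sizes the trial at 26 per group for "one-tailed significance of .025 and power of 80"%. Neither 11.1 nor 11.2 mentions an interim analysis or an adjustment for one.

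**End of enrolment.**
- Sections 3.1, 9.1 and 11.2 give 52.
- Sections 20.2 and 23.1 give 50, and 23.2 expects 40 of them to complete.
- Sections 3.1 and 20.2 give 2 years for recruitment, whereas 7.2 says "Approximately 18 months".
- Section 20.2 adds: "Oversampling will result in the desired target sample size at this rate". It gives no number.

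**The concern.** The .025 in 11.2 is the error rate of one test at a size fixed beforehand. It holds only if the decision to stop, extend or alter the trial does not depend on the comparison between arms. The plan does not secure that condition. The person who reviews cumulative data each month also helps to recommend protocol changes, efficacy outcomes are among the reviewed data, and no one is said to be blind to allocation. Participation lasts about 10 weeks (7.1), so post-treatment data will accumulate well before an enrolment of 18 to 24 months closes.

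The conflicting targets add to this. Closing at 40 completers, closing at 52, or going further under the heading of oversampling could each be defended from some section. A reader of the final report could not tell whether the size was settled without regard to the results. If it was not, the false-positive rate would exceed 2.5% and the estimated light effect would tend to be too large.

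**Working it through.** **1. The plan's own figure.** Inputs from 11.2: one-sided alpha .025, power 80%, 26 per group. The normal approximation is n per arm = 2(z₀.₉₇₅ + z₀.₈₀)²/d².
- d = 0.8: 2(1.960 + 0.842)²/0.64 = 24.5, so 25. The exact t calculation gives 26, with power 80.7%.
- d = 0.08, as printed ("Using a large effect size of .08"): 2,453.
- d = (85 − 70)/15 = 1: 16, or 17 by the t calculation.

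The 26 per group is therefore a single-look design at d = 0.8. That reading is assumed below.

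**2. Stated sizes and retention.** Retention is 80% (20.2, 23.2).
- 50 × 0.8 = 40 completers, 20 per arm.
- 52 × 0.8 = 41.6 completers, about 21 per arm.
- 52 completers need 52/0.8 = 65 enrolled, a figure that the protocol does not give.

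Power at d = 0.8 uses the noncentral t with 2n − 2 degrees of freedom and noncentrality d√(n/2):

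| Completers per arm | Noncentrality | Power |
|---|---|---|
| 20 | 0.8√10 = 2.53 | 69.3% |
| 21 | 0.8√10.5 = 2.59 | 71.6% |
| 26 | 0.8√13 = 2.88 | 80.7% |

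**3. Error rate if results by arm decided the end.** The check simulated a true null with a normal outcome and 1:1 arms. A one-sided two-sample t-test at .025 was repeated on accumulating data, with a stop at the first significant look. There were 200,000 trials per scenario, and the Monte Carlo standard error was at most 0.07 percentage points. The look schedules are assumptions, because the documents give none.

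| Looks | One-sided error | Constant one-sided p that would hold .025 |
|---|---|---|
| No arm comparison informs stopping | 2.5% | .025 |
| 40 and 52 completers | 3.6% | .017 |
| 40, 52 and about 65 (64 used) | 4.6% | .013 |
| Monthly from about 10 per arm to 26, over 18 or 24 months | 7.4–7.5% | .007 |
| Monthly from about 5–6 per arm to 26, over 18 or 24 months | 9.2–10.1% | .005 |

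The second row uses the protocol's own two completer counts. The third takes its upper end from 52/0.8. The last two need an unblinded test every month and a rule to stop on it, and no section describes either.

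**The case against.** A reader might infer that the monitoring team compares efficacy by arm each month, can change the protocol itself, and may end enrolment on a favourable result. The documents do not support that.
- Monthly efficacy review comes from joining 12.2, which has no frequency, to 12.6, which has no list of contents. Sections 12.5 and 12.6 describe quality and safety work.
- No section describes an arm comparison before the end. The team recommends changes; it is not said to make them.
- The accrual response in 12.1 is triggered by low accrual or retention, and 12.8 foresees no condition for immediate suspension.
- 52 and 50 are both set in advance. The 40 is the expected number of completers out of 50, not an optional stopping point. Oversampling is tied to retention, not to results.
- This is a pilot by its own description, so imperfect error control matters less than in a confirmatory trial.

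All of this stands, and it makes any inflation conditional. It does not close the gap: 12.2 names efficacy outcomes without limiting how they are viewed, 11.2 claims a specific error rate, and several end points are on paper. A stated purpose of checking quality is not a statement that the review is blind to arm.

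A practical objection also stands. Barring the PI from all efficacy data until lock would collide with the completeness checks in 11.4 and with the action on Epworth scores in 12.7. The remedy has to leave those in place.

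**Conclusion.** This is a missing safeguard together with inconsistent enrolment figures. It is not a stated procedure for optional stopping. If no comparison by arm influences the end of enrolment or a protocol change, the one-sided error is 2.5% as planned. If the choice between 40 and 52 completers followed the results, it would be about 3.6%. The 7% to 10% range is a hypothetical worst case and should not be read as an estimate for this trial. All these figures assume a normal outcome, equal arms and a t-test at .025 at each look.

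The inconsistency in size has a consequence that does not depend on anyone looking. With 40 completers, power is about 69% rather than 80%, if the effect size is read as 0.8.

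**What to change.** 1. In 12.2 and 12.6, state that until database lock the efficacy outcomes are reviewed only pooled or blind to arm. Keep the individual-level checks of completeness, accuracy and safety, including the Epworth score.
2. In 11.1, state that there is no interim efficacy analysis. If the sponsor wants one, specify the looks and an adjusted boundary; two looks at 40 and 52 completers would need a constant one-sided p of about .017.
3. In 12.1, state that protocol changes are recommended without sight of results by arm.
4. Choose one number randomised and one enrolment period, and use them consistently in 3.1, 7.2, 9.1, 11.2, 20.2 and 23.1–23.2. Replace the oversampling sentence with a number. Give the number as randomised, because consent comes before the apnea screen (9.2) and randomisation follows the pretreatment measures (3.2).
5. In 11.2, restate power for the number expected to complete. Either accept about 69% at 20 per arm, or randomise 65 to keep 52 completers.

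Items 1 to 4 cost only wording, and with the size fixed the .025 needs no adjustment. The PI gives up an early view of the efficacy trend by arm, for which the plan states no use. Item 5 costs recruitment only if 65 is chosen: 65 − 52 = 13 more people than the larger stated target.

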9.0 Procedures Involved

9.1 *Describe and explain the study design.*

This pilot study will include 52 lung cancer survivors using a 2X2 mixed model with Pre-Post assessments in two groups. Twenty-six participants will be randomized to red yellow directed light (control) and 26 participants will receive blue green (experimental) directed light therapy. The light source (Re-Timer) will be worn for 60-minutes every morning within 30-minutes upon awakening for 1-week. Participants will receive a weekly telephone call to ensure adherence to treatment plan and screen for safety/adverse events.

9.2 *Provide a description of all research procedures being performed and when they are performed, including procedures being performed to monitor subjects for safety or minimize risks.*

Screening for inclusion criteria includes a YES response to the following questions:

Are at least 21 years of age?

Do you have a diagnosis of non-small cell lung cancer stage I, II or III?

Have you had your lung cancer surgically removed at least 6 weeks ago, but not longer than 3 years ago?

Screening for exclusion criteria includes a NO response to the following questions:

Do you have any unmanaged medical or psychiatric diagnoses?

Are you currently pregnant?

Do you have a diagnosis of epilepsy?

Following informed consent, in order to rule-out sleep apnea as a confounder and assess for respiratory disturbance, all eligible participants will be screened for sleep apnea and hypoxia using the portable ApneaLink device for one night. Following a negative screen for sleep apnea, demographics, diagnoses, treatments, comorbidities, etc. will be recorded using the Demographics and Treatment Survey. Fatigue will be measured using the Functional Assessment of Chronic Illness Therapy Fatigue (FACIT) (Cella, Lai et al. 2011). Sleep continuity disturbance will be determined by Insomnia Severity Index (Bastien et al., 2001), 14-day sleep diary and the Epworth Sleepiness Scale (Johns 1991). Circadian activity rhythm disturbance will be assessed using the 14-day actigraph (Ambulatory Monitoring, Inc, Ardsley, NY) and Morningness-Eveningness Horne-Ostberg/Questionnaire (MEQ) (Horne and Ostberg 1976). Surveys and actigraphy will be performed at baseline and again after treatment ends. Expectation for treatment effectiveness will be assessed with the investigator developed Expectation Questionnaire before and

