after treatment. Treatment adherence and safety will be evaluated by self-report start/end time on sleep diaries and with weekly telephone/text reminders.

9.3 Describe procedures performed to lessen the probability or magnitude of risks.

Weekly telephone calls will be negotiated and utilized to identify Adverse Events and adherence, in addition to self-report adherence on sleep diaries.

9.4 Describe all drugs and devices used in the research and the purpose of their use, and their regulatory approval status.

Response:

- **Direct Light Therapy** - Re-Timer is a directed light device, worn like a pair of glasses that produces a 100% UV-free red-yellow (dim light-control) or blue-green (bright light-experimental), which may improve sleep and reset circadian rhythms. Regulatory status: classified as a wellness device (no FDA classification as medical device)
- **ApneaLink** – ApneaLink is a compact, lightweight, portable device used for overnight screening for sleep apnea, providing information about respiratory effort, pulse, oxygen saturation, nasal flow and snoring. Regulatory status: approved (FDA)
- **Actigraphy (Ambulatory Monitoring, Inc., Ardsley, NY)** – is a wrist worn device that uses a piezoelectric sensor that generates a signal based on movement. The analog signal is then digitalized and for each 1-minute epoch an activity count is calculated and stored. Software application allow for objective sleep-wake patterns (total sleep time, sleep latency, wake after sleep onset, number of awakenings, sleep efficiency) and circadian activity rhythm assessment (mesor, amplitude, acrophase, etc.). Regulatory status: approved (FDA)

9.5 Describe the source records that will be used to collect data about subjects. (Attach all surveys, scripts, and data collection forms.)

- **Demographics and Treatment Survey:** A general demographics questionnaire used to assess personal (age, gender), lifestyle (smoking history and current use of tobacco, stimulants, and alcohol), disease (stage and type of lung cancer) and treatment (schedule, type and dose of chemotherapy, other medications used and side effects) factors.
- **Functional Assessment of Chronic Illness Therapy Fatigue (FACIT) (Cella, Lai et al. 2011)** – The FACIT Measurement System is a part of a collection of quality of life questionnaires targeted to the management of chronic illness. FACIT has 13-items with a 5-point Likert scale with well established validity and reliability to assess fatigue.

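### Section 12.7 acts on a daily sleepiness score of 3 or higher, but Sections 12.2 and 12.3 differ on how often the score is monitored, and the reviewed text gives no route to staff before the weekly contact

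*Combined protocol and SAP*

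**What the plan says.** **Hazard.** Section 12.3 explains why sleepiness is tracked: "Daytime sleepiness may be hazardous for patients at risk for falling asleep while driving, for example".

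**Trigger.** Section 12.7 acts on an Epworth score above 10, or when a participant "scores a 3 or higher on the daily sleepiness scale, we will discuss this result with the participant". The stated purpose is to judge whether the person is at risk of harm, and more frequent monitoring follows. No time limit is set for the discussion.

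**Monitoring frequency.** Section 12.2: "Daytime sleepiness will also be evaluated daily, but monitored weekly". Section 12.3 says that the safety question is monitored "daily and assessed weekly by telephone with the participant".

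**Staff contact.** The scheduled contacts are weekly throughout:
- Section 9.1: "Participants will receive a weekly telephone call to ensure adherence to treatment plan and screen for safety/adverse events".
- Section 9.2: "Treatment adherence and safety will be evaluated by self-report start/end time on sleep diaries and with weekly telephone/text reminders".
- Section 9.3: "Weekly telephone calls will be negotiated and utilized to identify Adverse Events and adherence".
- Section 12.4: "Data collection will be conducted approximately weekly, to include a safety question".

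**Oversight.** Section 12.1 assigns safety monitoring to the principal investigator and a safety officer. Section 11.10 makes the principal investigator and research assistant responsible for receiving data. Section 12.6 has cumulative data reviewed monthly.

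**The concern.** A trigger on a daily score is useful only if someone who can act on it learns of the score soon after it is given. Here the participant rates every day, while each contact at which staff are described as hearing about it comes once a week. The Epworth does not fill the gap. It is given at baseline and at the end of the study, and Section 9.5 describes it as a measure of trait sleepiness. The daily rating is the only described measure that could pick up new sleepiness between calls.

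Treatment lasts one week, so about one call falls within it. A score of 3 early in treatment might be discussed only as treatment ends. Those most exposed are participants with no earlier trigger, because a baseline Epworth above 10 already brings discussion and closer monitoring. What is at stake is participant safety. Sample size, power and the efficacy comparison are not involved.

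**Working it through.** The plan states no time from score to review, so there is no figure of its own to reproduce. The check has two parts.

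**1. The passages side by side**

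| Section | Participant's rating | Staff action |
|---|---|---|
| 12.2 | daily | monitored weekly |
| 12.3 | daily | monitored daily, with a weekly telephone assessment |
| 12.4 | – | roughly weekly collection, including a safety question |
| 9.1, 9.2, 9.3 | – | weekly call, or telephone/text reminder |
| 12.7 | daily scale | discussion and closer monitoring at 3 or higher, no time limit |

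Sections 12.2 and 12.3 cannot both describe staff monitoring. If Section 12.3 means that staff see each score daily, the wait nearly disappears, but the reviewed text gives no mechanism for this. What it does describe points to slower receipt: a folder of pretreatment instruments completed at home (Section 3.2), return mailers (Section 20.2) and surveys carried by the principal investigator (Sections 11.11 and 24.5).

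**2. The wait if Section 12.2 governs**

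Assumptions: one score per day, scores seen only at the contact, and a contact every k days.

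- Call-day score recorded before the call: waits are 0 to k − 1 days, once each per cycle, with mean (k − 1)/2.
- Call-day score recorded after the call: waits are 1 to k days, with mean (k + 1)/2.

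| k | Rated before call: range, mean | Rated after call: range, mean |
|---|---|---|
| 5 | 0–4, 2.0 | 1–5, 3.0 |
| 7 | 0–6, 3.0 | 1–7, 4.0 |
| 10 | 0–9, 4.5 | 1–10, 5.5 |
| 14 (one call missed) | 0–13, 6.5 | 1–14, 7.5 |

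For k = 7 with the rating made before the call, 6/7 = 86% of scores wait at least 1 day and 4/7 = 57% wait at least 3 days. The weekday of the call makes no difference. The 5- and 10-day rows are illustrations, used because Section 12.4 makes the interval only approximate. The 14-day row is foreseeable because Section 12.2 tracks how many follow-up calls are accepted.

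**3. What a same-day report would change**

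Let p be the share of triggering scores that participants report the same day, with k = 7 and the rating made before the call.

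- If staff respond the same day, the mean wait is 3(1 − p): 1.5 days at p = 0.5 and 0.6 days at p = 0.8.
- If staff respond the next day, a reported score waits 1 day unless the call falls that same day, so its mean wait is 6/7 day. The overall mean is 3(1 − p) + 6p/7. At p = 0.5 this is 1.5 + 0.43 = 1.93 days; at p = 0.8 it is 0.6 + 0.69 = 1.29 days.

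Both values of p are illustrations; the documents give no basis for either. The gain depends on the staff response time as well as on the participant's report.

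**The case against.** The strongest reply is that Section 12.3 says the question is monitored daily. A reader who takes only the telephone half of that sentence might infer that the plan settles on weekly monitoring and that a delay of up to 6 days is established. The text does not support that. It contains two statements that conflict, and the delay follows only if Section 12.2 governs. What remains is that no daily mechanism is described, and that the assessment by telephone is weekly even in Section 12.3.

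Second, a reader might infer that participants are never told to call in. That cannot be concluded either. Section 13.1 refers to participants' responsibilities set out in the consent form, and Section 9.5 calls for surveys and forms to be attached. None of these was available for review, and an instruction to call would naturally sit there. This limits the claim to the text that could be read.

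Third, clinical importance is hard to judge. The instrument list in Section 9.5 has no entry for the daily scale, so its range and anchors cannot be seen, and a 3 might be mild or severe. Section 14.1 does not list sleepiness as a study risk, participants are screened for sleep apnea, and Section 12.1 rates the protocol as minimal to low risk. Weekly review could be a deliberate choice matched to that risk. This keeps the priority low. It does not explain why Section 12.7 places a trigger on a daily score and leaves the response time open.

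Fourth, a duty placed on the participant alone would not guarantee a prompt response, since Section 20.3 gives the research assistant 10 hours a week. That is right, and any fix needs a staff response time.

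**Conclusion.** The point stands as a low-priority, inexpensive safety improvement. Section 12.7 ties an action to a daily score, Sections 12.2 and 12.3 disagree on how often that score is monitored, and the reviewed text gives no route by which it reaches staff before the weekly contact.

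On the Section 12.2 reading, with strict 7-day contacts and one score a day, the longest wait is 6 to 7 days and the mean is 3 to 4, depending on whether the call-day rating comes before or after the call. A missed call extends the maximum to 13 or 14 days. On a working daily-monitoring reading of Section 12.3 the wait would be about 0 to 1 day.

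The documents do not show that any participant would be harmed or how often the trigger would be met, and they do not rule out an instruction in the consent form or attachments. Confidence is moderate for these reasons.

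**What to change.** Add one rule to Section 12.7, to the instructions given with the pretreatment folder, and to the device training in Section 3.2, identically for both arms:

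> *A participant who rates 3 or higher on the daily sleepiness scale phones or texts the study team that day; staff discuss the result by the next working day.*

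The folder instructions matter because Section 12.4 starts data collection around screening, whereas device training follows randomization.

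Then reconcile Sections 12.2 and 12.3 and keep the daily element, for example:

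> *Rated daily by the participant, scores of 3 or higher reported the same day, all scores reviewed at the weekly call.*

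Simply changing Section 12.3 to weekly would remove the more protective wording and shorten no wait. If the consent form or the diary already tells participants to call, Section 12.7 should repeat it and add the response time.

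The cost is a sentence in Section 12.7, an instruction at two existing contacts and a wording edit. No measure, visit or scheduled call is added. The downsides are occasional extra calls or texts that staff must answer by the next working day, a longer wait over weekends, and reliance on a sleepy participant to make contact. The weekly call remains as the backstop.
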